2.4 Sample Size Justification

2.4.1 Primary Endpoint

This trial will enroll 290 subjects that will be randomized in a ratio of 1:1 to either Reltecimod 0.50 mg/kg (n=145) or placebo (n=145), each in addition to standard of care. Sample size analysis was performed assuming that all patients will be evaluable for the primary endpoint. This assumption is justified on the basis of results from the Phase 2a trial and the Retrospective Study in which all patients were evaluable in terms of the definitions used to construct the NICCE endpoint.

The primary efficacy hypothesis will be tested using an unadjusted χ^2 statistic with an α =0.01 two-sided significance level. Statistical power was computed for a range of expected treatment group differences supported by the results of the preliminary studies noted above. For expected treatment group differences of 0.30, 0.25, and 0.20, statistical power will be 99%, 95.9%, and 80.2%, respectively. These power determinations were conservatively made assuming an average success rate between treatment groups of 0.5. In this way power estimates are applicable across the range of expected response rates; but may be conservative in some cases.

The use of NICCE and this range of expected treatment effects is supported by preliminary studies as summarized in the following table.

	Percentage Achieving NICCE	(n/N)
Phase 2a (mSOFA≥3) Reltecimod 0.50 mg/kg	71.4%	(5/7)
Phase 2a (mSOFA≥3) Placebo	20.0%	(1/5)
Retrospective Study (mSOFA≥3)	30.4%	(21/69)

In the Phase 2a trial, 71.4% (5/7) patients with baseline mSOFA≥3 treated with Reltecimod (at a dose of 0.50 mg/kg) achieved NICCE. In contrast, only 20% (1/5) of placebo patients with baseline mSOFA≥3 achieved NICCE, a difference of 51.4%. The Retrospective Study provides further support for the untreated response rate. Among 69 patients with baseline mSOFA≥3, 30.4% (21/69) achieved NICCE, a difference of 41.0% relative to Phase 2a patients in the 0.50 mg/kg treated group presenting with screening mSOFA≥3.

Given the selected sample sizes, if the observed differences in this study happen to be equal to 35%, 25%, or 20% (centered about 50%), then the corresponding 2-sided p-values will be

p<0.0001, p<0.0001, and p=0.0007, respectively. The observed difference will need to be larger than about 16% (e.g., 58% vs 42%) for p \le 0.01 (again assuming that the average success rate between groups is 50%).

2.4.2 Conditional Co-Primary Endpoint

Statistical significance for the co-primary endpoint will be evaluated using a two-sided type 1 error rate of α =0.05. The conditional co-primary endpoint (CCPE) will only be formally tested for superiority if the primary NICCE endpoint demonstrates Reltecimod superiority at p≤0.01.

Based on a similar evaluation of the preliminary studies discussed above, this study was designed to have very large statistical power for the conditional co-primary endpoint when the true expected CCPE success rates are 80% and 60% (difference of 20%) in the Reltecimod 0.5 mg/kg and placebo treatment groups, respectively. Under these assumptions power is 96.4%. However, if the true rates are 78% vs 62% (difference of only 16%), then power remains relatively high at 84.8%. The total sample size has also been selected to obtain sufficient enrollment on the treatment arm for relevant secondary effectiveness endpoints and for safety endpoints.

2.5 Randomization

290 patients will be recruited into the study and randomized to either Reltecimod 0.50 mg/kg or placebo in a 1:1 ratio. Randomization will be within site stratified by presence (+) of a diagnosis of Fournier's Gangrene versus absence (-) and whether the screening mSOFA score is >4 (+) or 3-4 (-) (See Tables 14.1.1.1 to 14.1.1.4). In the Retrospective Study analysis set with screening mSOFA \geq 3 (N=69), the median mSOFA value was 4 and 46.6% had values >4. Thus, the stratification for mSOFA is expected to roughly reflect a median split.

Four computer generated, blocked randomization lists will be provided for each site corresponding to the cross-tabulation of Fournier's Gangrene (+ vs -) and baseline mSOFA >4 (+ vs -) category status. Within each block, half of the assignments will be to active drug and half to placebo, in random order. Block sizes will be randomly varied as an additional masking feature.

The following will be done to insure balance through randomization. Every initial randomization code will end in '-1'. If a randomization code is used but the patient does not receive drug due to lack of confirmatory surgical NSTI diagnosis³, then the randomization code is not reused. Instead, the next patient from same stratum, (+,+), (+,-), (-,+), or (-,-) as the non-dosed patient, will receive the same allocation and the same randomization code except that the new code will end in '-2' while the old code ended in '-1'. In this way, randomization codes are not re-assigned which can cause confusion but the same drug allocation using the digits prior to the '-' are used, thereby preserving balance.

2.6 Analysis Sets

The following analysis sets are defined:

_

³ It is an unavoidable medical fact that NSTI diagnosis requires surgical confirmation and that randomization may occur prior to surgical confirmation in order for the treatment to begin at the optimal time frame. This presents the need to add a design feature that maintains within stratum balance; yet avoids the operational need for never applying the exact same randomization ID to more than one patient.

- Intent-to-treat (ITT): The ITT (Randomized) Set is defined as all randomized patients according to the intended study treatment.
- As-Treated (AT): The AT analysis set will include the subset of ITT patients who were exposed to study medication (active or placebo) and categorized according to the treatment actually received. This analysis set will be often referred to as the As Treated (Safety) Analysis Set.
- Modified Intent-to-treat (mITT): The mITT analysis set will include patients who were exposed to study medication and who had a definitive diagnosis of NSTI based on surgical verification. The mITT analysis set will be used in primary effectiveness analyses with patients assigned to their intended randomized.
- Per Protocol (**PP**): Optionally, a PP analysis set may be used in secondary effectiveness analyses. The PP analysis set would include patients in the mITT analysis set assigned according to actual treatment received rather than intended treatment; and excluding patients with one of the following:
 - 1. Significant violations of inclusion or exclusion criteria with a reasonably important potential to confound estimates of drug effects,
 - 2. Post randomization protocol violations with potential to confound estimates of treatment effects, or
 - 3. Patient death within 1 day of dosing.

Exclusions from the PP analysis set will be determined based on blinded clinical data. If a PP analysis set is defined, analyses will be limited to the subset of tables listed in Section 3.2 to be used in pre-planned exploratory sub group stratified analyses.

2.7 Futility analyses

A futility analysis will be performed based on the results of the first 100 patients (50 per group). The futility decision will be based on the predictive probability of eventual study success, conditioned on the data available at interim analysis. Independent, non-informative Bayesian prior distributions are assumed for the expected NICCE success rates for both treatment groups, namely, $\pi_{0.50} \sim \text{Beta}(1.1)$, $\pi_{\text{Placebo}} \sim \text{Beta}(1.1)$ for the active and placebo groups, respectively.

The Bayesian predictive probability of being able to demonstrate superiority of Reltecimod relative to placebo at a two-sided α =0.01 when the remaining patients are finally observed will be determined. The trial will stop enrollment for futility if this predictive probability is below a lower bound threshold of 10%.

The following table summarizes what the observed predictive probabilities will be as a function of magnitude of the treatment group difference and assuming an observed control success rate of 0.40. For example, if there are 20 success and 30 failures among placebo controls (40% success rate) at the interim analysis, then the futility boundary will be crossed if the number of active successes is 22 (44%) or less, that is, if the observed treatment group difference is 4% or less.

Diff	0.000	0.020	0.040	0.060	0.080	0.100	0.120	0.140	0.160	0.180	0.200	0.220	0.240	0.260	0.280	0.300
PP	0.029	0.050	0.082	0.127	0.187	0.261	0.348	0.444	0.543	0.639	0.728	0.804	0.866	0.913	0.946	0.969

The futility bound is 'non-binding' in the sense that no effort was made to 'recover' alpha to increase power.

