9.1.3 Futility Analysis

A futility analysis will be performed based on the results of the first 100 patients (50 per group). The futility decision will be based on the predictive probability of eventual study success, conditioned on the data available at interim analysis. Independent, non-informative prior distributions will be used for each parameter: $\pi_{0.50} \sim \text{Beta}(1,1)$, $\pi_{\text{Placebo}} \sim \text{Beta}(1,1)$. The Bayesian predictive probability of study success (i.e., two-sided $p \leq 0.01$) when the remaining patients are finally observed will be determined. The trial will stop enrollment for futility if the predictive probability of study success is below a lower bound threshold of 10%. The following table summarizes what the observed predictive probabilities will be as a function size of the treatment group differences and assuming an observed control success rate of 0.40. If there are 20 success and 30 failures among placebo controls (40% success rate), then the futility boundary will be crossed if the number of active success is 22 (44%) or less. The futility bound is 'non-binding' in the sense that no effort was made to 'recover' alpha to increase power.

Diff	0.000	0.020	0.040	0.060	0.080	0.100	0.120	0.140	0.160	0.180	0.200	0.220	0.240	0.260	0.280	0.300
PP	0.029	0.050	0.082	0.127	0.187	0.261	0.348	0.444	0.543	0.639	0.728	0.804	0.866	0.913	0.946	0.969

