2.2 Overall Study Success Criterion

The overall Study Success criterion, agreed upon with FDA, is to simultaneously observe p \leq 0.01 for the NICCE endpoint and p \leq 0.05 for the CCPE.

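### The futility rule is labelled as the predictive probability of study success but is computed for NICCE alone, so it overstates that probability and can let the trial continue below its own 10% limit when CCPE shows little or no difference

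*SAP*

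**What the plan says.** **The futility rule.** SAP 2.7 plans one look: "A futility analysis will be performed based on the results of the first 100 patients (50 per group"). It then states that "The futility decision will be based on the predictive probability of eventual study success". Only one endpoint is modelled: "Independent, non-informative Bayesian prior distributions are assumed for the expected NICCE success rates for both treatment groups". Only one final test is named: "The Bayesian predictive probability of being able to demonstrate superiority of Reltecimod relative to placebo at a two-sided" α of 0.01. The action is "The trial will stop enrollment for futility if this predictive probability is below a lower bound threshold of 10" per cent. Protocol 9.1.3 has the same rule and glosses study success, in parentheses, as two-sided p≤0.01.

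**The success criterion.** SAP 2.2 reads "The overall Study Success criterion, agreed upon with FDA, is to simultaneously observe" p≤0.01 for NICCE and p≤0.05 for CCPE. SAP 5.6 and 8.1 repeat this. CCPE (SAP 2.1.3) keeps the survival, debridement and amputation components of NICCE and drops the two mSOFA components.

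CCPE does not enter the futility calculation in either document. SAP section 1 says that the SAP governs where it differs from the protocol.

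**The concern.** The same term carries two meanings inside the SAP. The 10% limit is meant to be read against the chance that the study succeeds, but the number compared with it is the chance of passing the first of two required tests.

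The direction of the error is fixed. Every NICCE success is also a CCPE success, but significance on NICCE does not imply significance on CCPE. Requiring both can only lower the probability.

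The gap is widest when a drug moves organ-function scores but does little for survival, debridement or amputation. That pattern looks promising to the planned rule while the second required test is unlikely to be met. What is at stake is further enrolment of critically ill patients on a figure that the iDMC would take to be the chance of study success.

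**Working it through.** **Inputs**
- Interim: 50 per arm (SAP 2.7). Final: "randomized in a ratio of 1:1 to either Reltecimod 0.50 mg/kg (n=145) or placebo (n=145") (SAP 2.4.1). That leaves 145 − 50 = 95 per arm to be observed.
- Priors: Beta(1,1) in each arm (protocol 9.1.3). The SAP prints this as Beta(1.1); reading it as Beta(1.1,1.1) changes the table by at most 0.002.
- Final tests: unadjusted chi-square, two-sided 0.01 for NICCE and 0.05 for CCPE, in favour of active.
- Interim CCPE counts are not given in the documents. They are assumed below and varied. The base case for placebo is 30/50, from the planning rate of 0.60 (SAP 2.4.2).

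**Step 1: reproduce the plan's table.** With x interim NICCE successes in an arm, future successes follow a beta-binomial(95; 1+x, 51−x). The final statistic is z = (p_A − p_P) / √(2p̄(1−p̄)/145), where p̄ is the pooled rate. The predictive probability is the total probability of outcomes with z ≥ 2.576. For placebo 20/50 this gives 0.029, 0.050, 0.082 and 0.127 at active 20 to 23, then 0.728 at 30 and 0.969 at 35. All 16 printed entries match to three decimals, so the table is NICCE-only.

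**Step 2: joint predictive probability.** Let y be the interim CCPE successes in an arm. Draw p from Beta(1+x, 51−x) for NICCE and q from Beta(1+y−x, 51−y) for CCPE among NICCE failures. Draw A from Bin(95, p) and B from Bin(95−A, q). The final NICCE count is x+A and the final CCPE count is y+A+B. The joint value is the share of draws with z ≥ 2.576 on NICCE and z ≥ 1.960 on CCPE. For active NICCE 30/50 and CCPE 31/50, for example, p comes from Beta(31, 21) and q from Beta(2, 20).

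| Interim NICCE (active vs placebo) | Assumed interim CCPE | Rule | Joint |
|---|---|---|---|
| 30/50 vs 20/50 | 31/50 vs 31/50 | 0.73 | 0.08 |
| 30/50 vs 20/50 | 34/50 vs 31/50 | 0.73 | 0.25 |
| 30/50 vs 20/50 | 40/50 vs 30/50 | 0.73 | 0.70 |
| 25/50 vs 20/50 | 30/50 vs 30/50 | 0.26 | 0.06 |
| 23/50 vs 20/50 | 30/50 vs 30/50 | 0.127 | 0.04 |

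**Step 3: sensitivity.** A different prior, Dirichlet(1, 0.5, 0.5) over NICCE success, CCPE-only success and failure, also keeps NICCE at Beta(1,1). It gives the same picture: 0.043 at active NICCE 23/50 and 0.073 at 30/50, with CCPE 30/50 in each arm. At 23/50 with no CCPE difference, moving placebo CCPE to 26, 33 or 36 of 50 gives 0.056, 0.038 and 0.033. At 23/50 against placebo CCPE 30/50, the joint value passes 10% only at active CCPE 35/50 (0.110; 34/50 gives 0.099). At active NICCE 30/50 a single extra CCPE success is enough (31/50 vs 30/50 gives 0.114).

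**Step 4: simulated stopping at the 10% limit.** True rates are assumed, written active/placebo.

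| NICCE | CCPE | Planned rule stops | Joint rule stops |
|---|---|---|---|
| 0.60/0.40 | 0.70/0.70 | 7% | 56% |
| 0.40/0.40 | 0.60/0.60 | 69% | 80% |
| 0.60/0.40 | 0.80/0.60 | 6% | 8% |
| 0.60/0.40 | 0.78/0.62 | 6% | 11% |

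The planned rule depends on NICCE only, so 7% against 6% in the first column of results is simulation error. In the first row the probability of study success is about 3%. In the third row, changing to the joint rule lowers the probability of study success from 78.8% to 77.9%. In the fourth row the loss is about 2 points (73.1% to 71.4% in one run, 72.6% to 70.2% in another).

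**The case against.** The strongest reply is that the rule is fully specified. The protocol says in parentheses what it means by study success, the SAP names NICCE and α = 0.01, and CCPE is tested only after NICCE succeeds. Basing futility on the first test in a sequence is a recognisable choice, so what remains is a label. Part of this stands: a programmer would not misapply the rule, and renaming the quantity would remove the contradiction. But the SAP governs, it does not carry the protocol's parenthesis, and its own definition of success is the joint one. An iDMC reading the stated purpose would take the number for something it is not.

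The scenario with a full 20-point NICCE effect and no CCPE effect is also demanding. Among CCPE successes it needs 0.60/0.70 = 86% against 0.40/0.70 = 57% to meet the mSOFA criteria. The Phase 2 summary (protocol Table 3) shows mortality and the share with four or more debridements moving the same way as SOFA. That stands as a reason to think the scenario unlikely, not to leave it unguarded.

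There are mitigations. The bound is described as non-binding, the iDMC may request further unblinded data (protocol 9.1.4), and its charter, which is to hold decision rules, is not among the documents. Continuing also has value for secondary and safety endpoints (SAP 2.4.2) and for the safety population of the marketing application (SAP 1.1). However, SAP 2.7 uses non-binding only to mean that no alpha was recovered, and it still says that enrolment will stop.

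A reader might infer that a drug acting only on mSOFA cannot succeed. The figures do not support that: study success is about 3% in the first simulated row, and at NICCE 30/50 vs 20/50 three more active CCPE successes raise the joint value from 0.08 to 0.25. A reader might also infer that 290 − 100 = 190 further patients would be enrolled needlessly. That is an upper limit. The look follows 28 days of follow-up in 100 patients (protocol 8.7) and no recruitment pause is stated, so some of them would be enrolled before any decision.

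**Conclusion.** The point holds in a conditional form. The planned quantity is not the probability of study success as the SAP defines it. It is always at or above that probability, so the rule can continue too readily but never stops a trial whose joint value is 10% or more.

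The size depends on CCPE. When CCPE tracks NICCE the two values nearly agree (0.73 and 0.70), and at the planning rates stopping differs by only 2 to 5 percentage points. When neither endpoint differs, the planned rule stops 69% of trials and the joint rule 80%. The large gap, 7% against 56%, needs a strong NICCE effect with no CCPE effect. It would be wrong to infer that the trial will generally run on below the limit. It can do so when NICCE is favourable and CCPE shows little or no difference.

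Nor does the mismatch inflate type I error, since there is no stop for efficacy. The joint figures rest on assumed interim CCPE counts and true rates; the reproduction of the printed table does not.

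**What to change.** In SAP 2.7, protocol 9.1.3 and the iDMC charter, define the futility quantity as the predictive probability that NICCE p≤0.01 and CCPE p≤0.05 are both met at 145 per arm. One workable specification is Beta(1,1) for NICCE and Beta(1,1) for CCPE among NICCE failures, in each arm. Keep the 10% limit and report the NICCE-only value beside the joint one. Replace the printed table with one that varies both endpoints.

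No new data are needed, because the three CCPE components are already NICCE components. The cost is a little programming for the unblinded statistician, about 1 to 2 points lower probability of study success at the planning rates, and a few more stops there (6% to 8%, or 6% to 11% with CCPE 0.78/0.62).

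If the sponsor prefers to keep the NICCE-only rule, the minimum is to stop describing it as the probability of study success, say that it addresses NICCE only, and give the iDMC the joint value as well.

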2.8 Control of blinding and DMC

2.8.1 Randomization and Unblinded Study Statistician

There are three statisticians in this study with different roles:

Blinded primary study statistician – primary lead statistician

Unblinded study statistician – performs randomization and provided back-up

Unblinded DMC statistician independent statistician supporting DMC operations

The role of the unblinded study statistician is:

Perform final randomization,

Provide the randomization to the pharmacy vendor,

Provide randomized allocations in electronic form to the unblinded DMC statistician,

Serve as a backup unblinded statistician.

In advance of study initiation, programming for the blocked randomized treatment allocation with randomized block size was developed. The program to perform this randomization was written in SAS with a Proc IML call to R and is provided in Appendix 6.

A preliminary randomization 'test' seed was used to generate a set of preliminary randomization ID numbers. These were exported to site-specific Excel files and also summarized in a single SAS listing report (RTF format). The unblinded study statistician will use this program to determine final (blinded) randomized allocations and will provide these to the contract drug dispenser in an agreed upon format. A variable indicating the blinded treatment allocations will not be part of the clinical study data to be managed by the data management CRO. This is to eliminate any risk of unblinding through inadvertent data transfer. Therefore, only blinded study data will be available to the blinded primary study statistician and blinded analysis staff.

2.8.2 Data Monitoring Committee and Unblinded DMC Statistician

A Data Monitoring Committee (DMC) will be utilized in this study which will be reviewing safety outcomes at a prescribed regularity in addition to helping to facilitate the unblinded futility analysis. The Charter will provide decision rules, composition of the DMC members and their conflict of interest statements. This DMC will include an *unblinded DMC statistician*.

Analysis staff under the direction of the primary study statistician will develop SAS based programs that process clinical data provided by the blinded data management CRO to populate planned safety analysis tables and listings, but in a blinded fashion. This includes using a pseudo randomization for purposes of table generation program development. This programming and relevant data will be provided to the independent unblinded DMC statistician.

As mentioned above the *unblinded study statistician* has limited roles for this study. This individual will perform the final randomized allocation and will provide the unblinding codes to

the unblinded DMC statistician who will run programs to populate selected tables in an unblinded fashion. If needed, the unblinded study statistician may work with the unblinded DMC statistician to resolve difficulties and can serve as a backup unblinded statistician if needed.

The independent unblinded DMC statistician will perform the necessary computations involving the Bayesian predictive power to be used in the planned futility assessment at the planned interim analysis based on the results from the first 100 evaluable patients.

3 Description of Variables to be Included in Statistical Analyses

3.1 Medical and Surgical History

Details of the NSTI will be recorded on the case report form (CRF) and include: "clinical diagnosis" (as a specific subset of NSTI) at the time of enrollment; location of primary infection; date of onset, identified predisposing factors (trauma, surgery, IV drug use, and co-morbidities such as diabetes or vascular insufficiency; prior surgical procedures related to the etiology of the NSTI; prior surgical procedures for the treatment of the primary infection site; antimicrobial use from the date of onset of current illness if available [may predate diagnosis of NSTI]). A medical history identifying active medical or surgical conditions will be reported on the CRF. All chronic medications will be identified and characterized by dose and frequency as well as reason for use.

